4.15 Monitoring Fidelity (Feasibility)

All trial treatment sessions will be video recorded and a random sample (1 in 6) will be selected by the PI for analysis. A small and unobtrusive video camera will be used to do this. To avoid observer bias, the treating therapists will be asked to set up the video camera for each session. The sample will be analysed using a previously validated method, and will be compared for coherence with the written records of the treatment session.

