4.5.3.2 Process for Gaining a Consultee Declaration

If a potential participant is deemed unable to consent to the study (i.e. they lack capacity), then a personal consultee (usually the next of kin) will be asked to consider whether they would be willing to provide consent on their behalf, based on the presumed wishes of the potential participant.

The full version of the Participant Information Sheet will be shared with the identified consultee, along with the Easy Read PIS. If they are willing to do so, they will be asked to sign the consultee declaration form, on behalf of their relative/friend.

In the event that a personal consultee cannot be found for someone who is deemed to lack capacity, a professional consultee would not be used. In these circumstances, the person lacking capacity would not be able to participate in the study.

At all times, the wishes of the participant will be upheld. For example, they will not be video recorded if they express that they do not wish for this to happen.

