4.6 Trial Flowchart

4.7 Intervention

All mobility focussed rehabilitation sessions will utilise the ILA, as usual care. This includes rehabilitation (delivered by a physiotherapist, occupational therapist or therapy assistant) that focusses on sitting, sit to stand, standing, stepping, transfers and walking. The content of therapy will be based on the treatment guidelines and intervention manual, which have been developed by an international expert group (using Delhi methodology). As this is a clinically grounded, pragmatic trial, therapists will have freedom to tailor the specific content of each treatment session to patient need, whilst remaining true to the ILA. Other therapy interventions, such as upper limb rehabilitation, will be provided as usual. Whilst the content of this additional therapy will not be monitored, the quantity of other therapy, outside of the trial interventions, will be recorded and compared between groups. Frequency of treatment will be based on the usual practice of the treating hospital. The actual number of sessions received by each participant will be recorded.

Specific details relating to the IMPS intervention will be shared with intervention sites, once randomisation has taken place. Standard care sites will continue to delivery rehabilitation as normal, but will be asked to recruit eligible patients for data collection. An overview is given in table 1.

	Control Group Standard Care*	Experimental Group Implicit Learning Approach
Quantity and Frequency of Coaching Statements (Instructions and Feedback)	HIGH 
 Instructions given at the beginning and throughout the task (i.e. during practice) Feedback given during task practice – at least once for every 5 repetitions of any given task 	LOW 
 Instructions only given at the beginning of task practice Feedback or further instruction avoided throughout task practice
Focus of Attention	INTERNAL Direct attention to the action itself. Use the term “focus on [a reference within the body]”. Example: “Bend your knee and lift your foot onto the block. Focus on moving your leg”	EXTERNAL Direct attention to the effects of the action. Use the term “focus on [a reference in the environment]” Example: “Step onto the marker on the block. Focus on the marker”

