7.1 Assessment of Safety

7.1.1 Expected ILA Adverse Events

Although unlikely, there is a possibility that the ILA is perceived as less personal/motivating for patients, and this may be associated with a reduced willingness to participate in therapy. We will monitor adherence with rehabilitation across all sites. Non-compliance will be considered an AE if (i) a patient is declining to participate in rehabilitation sessions over a period of 5 days and (ii) the clinical team are unable to account for this in any other way. This will be addressed on an individual basis through discussion with the patient and the clinical team. If indicated, they will be withdrawn from the study.

If the treating team have any concerns about using the ILA with an individual patient, for example, should they feel that a patient is not responding /recovering as expected, they should discuss this with the Chief Investigator. If indicated, the participant will be withdrawn from the study, and their rehabilitation will revert to standard care. This decision will be taken on an individual basis, following discussion with the clinical team, Chief Investigator and (if appropriate) the participant. Withdrawal due to unanticipated/unexplained lack of progress in rehabilitation will be considered an AE.

It is important to note that, whilst therapists at the intervention sites are encouraged to adhere as much as possible to the ILA guidance, this is a pragmatic trial, and they can use their own clinical judgement during each individual treatment session. This is monitored as part of the feasibility aspect of this trial.

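### Fidelity sampling relies on filming by the therapists being assessed and a draw made by the PI, and no planned check would show which sessions went unfilmed

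*Combined protocol and SAP*

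**What the plan says.** Section 4.15 sets out the fidelity sample: "All trial treatment sessions will be video recorded and a random sample (1 in 6) will be selected by the PI for analysis". On who films, it says that, as a guard against observer bias, "the treating therapists will be asked to set up the video camera for each session". The analysed recordings "will be compared for coherence with the written records of the treatment session"; that check applies to the drawn sample.

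Other sections bear on the same procedure:

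- **Synopsis and 6.1.** Fidelity is part of the primary objective. Section 6.1 accepts that it may fall short and treats it as a key feasibility question.
- **4.16.** Fidelity is measured as the mean number of coaching statements per person, split into internal and external focus, and compared between groups with a 95% confidence interval.
- **4.7.** "The actual number of sessions received by each participant will be recorded". This is a count; no dated list of sessions is described.
- **4.5.3.2.** On participants entered through a consultee: "they will not be video recorded if they express that they do not wish for this to happen".
- **7.1.1.** Of therapists at intervention sites: "they can use their own clinical judgement during each individual treatment session". The same section says this is monitored as part of feasibility.
- **8.1.** Recordings are handed to the PI on a memory card.
- **4.5.3.1 and 5.1.** PI means a site role in the first and the study interviewer in the second.

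**The concern.** Video is the only direct measure of what therapists actually say. Whether a session reaches the video record depends on the therapist under assessment, who is asked, but not otherwise checked, to set up the camera. Section 7.1.1 allows departures from the ILA within a session, and those are the sessions that monitoring most needs to capture. A therapist planning such a session may be less likely to film it.

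The plan intends complete filming but does not say how completeness will be verified, how missing or failed recordings will be counted, or how the random draw will be generated. Since the footage goes to the PI and the PI makes the draw, the natural reading is that the sampling frame is the footage received. A random draw from an incomplete frame describes only the filmed part, and comparing drawn recordings with their written records cannot bring an unfilmed session to light.

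At stake is one half of the primary objective. A favourable fidelity result could not be told apart from selective capture when the Phase III trial is designed.

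**Working it through.** **Inputs.** From the documents: intended filming of all sessions, a sampling fraction of 1 in 6 (4.15), 60 participants (4.13), and the coaching-statement measure (4.16). The documents do not give the share of sessions that will be filmed, the difference between filmed and unfilmed sessions, or the number of sessions per participant. Values for these below are assumptions.

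**Step 1: the plan as written.** There is no fidelity sample size or precision figure to reproduce. If every session is filmed and the draw is random, selection bias is zero.

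**Step 2: incomplete filming.** Let f be the share of sessions filmed, and let m_F and m_U be the mean of the fidelity measure in filmed and unfilmed sessions, with sessions weighted equally.

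- Mean over all sessions = f × m_F + (1 − f) × m_U
- Mean the trial would report = m_F
- Bias = (1 − f) × (m_F − m_U)

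**Step 3: assumed values.** Take the share of statements that are externally focused, on a 0 to 1 scale.

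| Filmed share f | Gap m_F − m_U | Bias |
|---|---|---|
| 1.0 | any | 0 |
| 0.9 | 0.20 | 0.1 × 0.20 = 0.02 |
| 0.8 | 0.20 | 0.2 × 0.20 = 0.04 |
| 0.7 | 0.40 | 0.3 × 0.40 = 0.12 |
| 0.5 | 0.40 | 0.5 × 0.40 = 0.20 |
| 0.8 | 0 | 0 |
| 0.8 | −0.20 | 0.2 × (−0.20) = −0.04 |

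The same formula applies to the number of statements. There the flattering direction is downward, because the ILA calls for fewer statements.

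**Step 4: the between-group comparison.** The bias in the difference is the ILA-arm bias minus the control-arm bias. With f = 0.8 and a gap of 0.20 in the ILA arm and complete filming in control, it is 0.04 − 0 = 0.04. With the same loss and gap in both arms it is 0.04 − 0.04 = 0. What matters is whether non-filming differs by arm.

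**Step 5: would it be seen?** Suppose 10 sessions per participant (assumed) and f = 0.8.

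- Delivered: 60 × 10 = 600. Filmed: 0.8 × 600 = 480.
- Draw from footage: 480 / 6 = 80 videos, with no sign of the 120 missing sessions.
- Draw from a list of delivered sessions: 600 / 6 = 100, of which about 20 would be expected to have no video and 80 to be codable.

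The coding load is about the same, but only the second draw shows the gap. The count in 4.7 would allow filmed and delivered totals to be compared, but no such comparison is planned.

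**The case against.** A reader might infer that therapists choose which sessions to film, that the PI picks which ones to analyse, and that ILA delivery will therefore be overstated. The documents do not support this. Section 4.15 covers all trial sessions, gives therapists no discretion over filming, and calls the sample random. Having therapists set up the camera has a stated purpose, to avoid observer bias, and that is a reasonable choice. The camera is set up for a session, so filming is ordinarily settled before anyone knows how it went, and no section describes recordings being stopped or discarded.

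The direction is also unproven: Step 3 gives zero or a reversed sign when unfilmed sessions are no different or better. Sections 6.1 and 7.1.1 acknowledge imperfect fidelity and promise monitoring. The statement on not recording in 4.5.3.2 sits in the consultee section, while 4.5.3.1 and 4.5.3.4 point to non-enrolment or withdrawal of people unwilling to take part in any element, so unfilmed participants may be few. Nothing shows that a PI's random draw would be compromised.

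All of this stands, and it limits the point to a conditional risk. It does not remove the gap: complete filming is an intention that nothing verifies, a planned departure from the ILA could still affect whether the camera is set up, and the promised monitoring depends on the same recordings.

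**Conclusion.** The point holds as a conditional risk and a cheap improvement, not as an error in the plan as written. If filming is incomplete and related to delivery, the coaching-statement comparison in 4.16 could be biased, and no planned check would reveal it. Upward bias in ILA fidelity is the more plausible direction: intervention-site therapists are trained and hold the manual (4.10), so they know the standard, while control units do not know the intervention's detail (4.2, 4.8). It cannot be proved from the documents.

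The size cannot be derived either. The values in Step 3, from −0.04 to 0.20, rest wholly on assumed filming shares and gaps. A reader might wish to quote an overstated percentage of ILA sessions delivered, or to count unfilmed sessions as not delivered. Neither fits: 4.16 reports statements per person and defines no session-level delivery percentage, and the second would class a session left unfilmed at the participant's wish as a fidelity failure.

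**What to change.** In 4.15:

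1. Have the trial statistician draw the 1-in-6 sample by computer, stratified by unit, from a dated list of all delivered trial sessions, in place of a draw by the PI from the footage received.
2. Record any drawn session without usable video as *not filmed*, with the reason, separating participant refusal from other reasons.
3. Report sessions filmed over sessions delivered, by unit and arm, beside the fidelity result.
4. If unfilmed sessions are not rare, add a sensitivity analysis on the coaching-statement scale in both arms. For example, assign unfilmed ILA sessions the statement counts from the same unit's pre-randomisation recordings (4.3). Those are only 6 to 10 sessions per site, chosen by non-probability sampling, so the result is indicative.

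**Cost.** Sites must keep a dated session list, which goes beyond the count in 4.7, and send it to the statistician. The number of videos coded stays about the same. The fidelity result may look less favourable.

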4.16 Analysis

Data will be stored and managed using SPSS. Statistical support will be provided by the University of Southampton. Double data entry will be used for paper-based assessments.

The unit of analysis is the individual patient. As this is a pilot study, analysis will primarily be descriptive. Descriptive methods will be used to estimate feasibility of factors relating to the protocol, such as recruitment (proportion of eligible people who consent to the study) and retention (completion of outcome measures at 4 weeks).

Fidelity of the interventions will be established by comparing the number and type of coaching statements delivered to each group. We will describe the mean number of coaching statements per person (and the breakdown of these statements as externally- or internally-focussed) in each group. While we expect large differences, we will not formally test the difference as the study is not designed to do so; we will instead provide an estimate of the difference with corresponding 95% confidence interval. Differences in outcome and potential effect size for the Fugl Meyer, SwePASS and mRMI will be calculated using confidence interval estimation.

5 Process Evaluation

To enable us to understand patient and therapist perceptions and experiences of the ILA, will we be inviting a sub-set of participants to take part in a qualitative evaluation of the ILA.

5.1 Patient Interviews

We will invite 20 participants (10 from the intervention arm and 10 from the control arm) to take part in a semi-structured interview. These will be carried out within 1 week of the final treatment session to ensure that the intervention is recent enough for the patient to recall.

Interviews will be conducted by the Principal Investigator (PI). They will focus on patients' experiences of therapy and their perceptions of the benefits and disadvantages of the therapeutic style received. They will take place whilst the patient is in hospital or following their return home, will last for around 45 minutes, and will be audio recorded. Where necessary to comply with COVID-19 restrictions, interviews will be conducted remotely, over the telephone or via video call.

We will use maximum variation sampling to identify the sample, to include those with differing stroke severities (including differing levels of language and cognitive impairments), ages, gender and family/care situations.

Separate informed consent will be sought for the interview; participation in the clinical trial will not be dependent on participation in this qualitative evaluation. Participants from 4 of the clusters will be included.

5.1.1 Consent Process for Interviews that are conducted remotely

Where the patient remains an inpatient, the interviewer will liaise with the patient via the clinical team, to agree a mutually convenient date, time and method (phone or video call) for the interview.

Where the patient has returned home, the clinical team will pass the patients name and contact details to the researcher, after seeking permission from the patient to do so. The researcher will then contact the patient to explain more about the interview, and to agree a mutually convenient date, time and method (phone or video call) for the interview.

On the day of the interview, consent will be sought verbally. After discussing details of the purpose and nature of the interview, the researcher will inform the participating that the call is being audio recorded, and will then read each statement on the consent form, which they will seek verbal consent for. The researcher will then sign the form, and two copies will be sent to the participant via post. They will be asked to sign and return one copy in a pre-paid envelope. Audio recording will capture the verbal consent process.

5.2 Therapist Discussion Groups

Four discussion groups, (one at each *intervention* site), involving therapists who took part in the study, will take place at the end of the trial, after all treatment sessions have been delivered. All therapists and therapy assistants who are involved in delivering the ILA will be invited to take part. The insights gained from the discussion groups will give us a more valid understanding of the potential application of the Implicit Learning Approach in clinical practice.

6 Ethical Issues

6.1 Cluster Randomised Design

The cluster randomised design presents its own unique ethical issues. Rather than individual patients providing consent prior to randomisation, whole Stroke Units (clusters) will be randomised to either the Implicit Learning Approach or control. Consent to participate in the study and be randomised will be given at Stroke Unit level, by a cluster guardian.

Individual patients who meet the inclusion criteria, will be asked to give consent to take part in the trial, to have their data included in the study, and to complete additional measures.

For units randomised to the ILA, therapy teams will be asked to adopt the ILA for participants who have agreed to take part in the trial. For all other patients on that Unit, they will continue with standard care. However, because the therapists will have been trained in the ILA, and will be using it with trial participants, there is the possibility that elements of the ILA drift into the rehabilitation of non-trial patients. Given that implicit learning approaches are used in standard practice already, it is acceptable that therapists may adopt elements of the ILA for non-trial patients. This is entirely within their own professional autonomy and clinical judgement.

This cluster randomised approach has been chosen to ensure fidelity of the intervention, and therefore to ensure that the study is most likely to provide useful insights and data - this in itself is ethically important. From an ethical point of view, this design is justifiable because:

- Current therapy practice includes both implicit and explicit behaviours. These are not therefore novel or experimental concepts. This research is delineating two approaches already in use, to answer important questions about the effectiveness of each.
- There are no significant risks to those individuals who will receive the ILA.
- Only patients who provide consent to take part will receive the full ILA.

No Unit will use the ILA wholly as its approach, and therefore there is still a risk that fidelity isn't maximised for the trial participants. This is an accepted limitation at this stage – it will be closely monitored in the study, and is one of the key feasibility questions.

7 Monitoring

7.1 Assessment of Safety

7.1.1 Expected ILA Adverse Events

Although unlikely, there is a possibility that the ILA is perceived as less personal/motivating for patients, and this may be associated with a reduced willingness to participate in therapy. We will monitor adherence with rehabilitation across all sites. Non-compliance will be considered an AE if (i) a patient is declining to participate in rehabilitation sessions over a period of 5 days and (ii) the clinical team are unable to account for this in any other way. This will be addressed on an individual basis through discussion with the patient and the clinical team. If indicated, they will be withdrawn from the study.

If the treating team have any concerns about using the ILA with an individual patient, for example, should they feel that a patient is not responding /recovering as expected, they should discuss this with the Chief Investigator. If indicated, the participant will be withdrawn from the study, and their rehabilitation will revert to standard care. This decision will be taken on an individual basis, following discussion with the clinical team, Chief Investigator and (if appropriate) the participant. Withdrawal due to unanticipated/unexplained lack of progress in rehabilitation will be considered an AE.

It is important to note that, whilst therapists at the intervention sites are encouraged to adhere as much as possible to the ILA guidance, this is a pragmatic trial, and they can use their own clinical judgement during each individual treatment session. This is monitored as part of the feasibility aspect of this trial.

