4.5.3.4 Process if a participant loses capacity during the study

[figure not shown]
Although unlikely, a participant who gave informed consent at the point of recruitment, may lose capacity during the course of the research. It is likely that any loss of capacity at this stage reflects medical instability - such as a further stroke, or an infection.

The study will adhere to the principles, as laid out and defined in the Mental Capacity Act (2005). At the time of the person consenting to the trial, they have expressed a wish to participate. Therefore, the person will remain in the study, as long as it is appropriate clinically, and there is no observable or communicated evidence that they do not wish to continue.

If the individual is communicating that they do not wish to continue in the trial, or are demonstrating an unwillingness to participate in any of the trial interventions (e.g. assessments, video recording, or therapy treatment sessions), then they will be withdrawn

The most likely cause of loss of capacity is a further stroke, or another medical event. In these circumstances, then (irrespective of capacity) the person will not be clinically appropriate to remain in the trial, and will be withdrawn.

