4.10 Training for Intervention Sites

For sites randomised to the intervention arm, all physiotherapists, occupational therapists and therapy assistants will be trained in the ILA. Training is anticipated to last no more than 3 hours. Additional training sessions will be offered if new members join the team during the recruitment phase. A manual including written, photographic and video resources will demonstrate how to adapt standard care interventions to the ILA. Therapists will be able to refer to the manual throughout their involvement in the study.

Whilst the wider multidisciplinary team (e.g. nurses, doctors, other AHP's) will not specifically be asked to change their approach with patients, those at intervention sites will be invited to attend a short education session to raise their awareness of the trial, and will be provided with written information about the study, and the concepts under investigation. As these professions wouldn't typically be analysing movement or giving specific instructions/feedback, this level of engagement is deemed appropriate and realistic.

The therapy team will be encouraged to give the MDT (particularly nurses) specific guidance about how to instruct an individual patient during movement (as part of a manual handling care plan, and in line with the ILA approach). These awareness raising sessions will support the MDT to understand and follow through these instructions.

As part of the training, clinical staff will be reminded of the options to withdraw participants from the study, should there be concerns about the impact the ILA has on their recovery (see 7.1.1).

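### Five-day refusal of therapy counts as an adverse event only if the unblinded clinical team has no other explanation, so the counts are probably incomplete and not like-for-like between arms

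*Combined protocol and SAP*

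**What the plan says.** Section 7.1.1 of the combined protocol and SAP, on expected ILA adverse events, gives the reason for watching refusal: "there is a possibility that the ILA is perceived as less personal/motivating for patients", which may make patients less willing to take part. It adds: "We will monitor adherence with rehabilitation across all sites". Refusal becomes an AE only when two conditions are both met. The first sets a duration: "i) a patient is declining to participate in rehabilitation sessions over a period of 5 days". The second is a causal filter that the treating staff apply: "ii) the clinical team are unable to account for this in any other way".

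Other sections bear on how that rule would work:

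- **Who judges.** At intervention sites, "all physiotherapists, occupational therapists and therapy assistants will be trained in the ILA" (section 4.10). Section 4.12 says the research practitioner is not blind. Section 4.11 describes blinding for outcome assessors and participants only, and no blinded review of AEs is described.
- **What is logged.** Section 4.7 says: "The actual number of sessions received by each participant will be recorded". It leaves treatment frequency to each hospital's usual practice, and section 4.9 lets treatment run for the whole inpatient stay.
- **Withdrawal.** Under section 4.5.3.4, a participant who has lost capacity and is "demonstrating an unwillingness to participate in any of the trial interventions (e.g. assessments, video recording, or therapy treatment sessions), then they will be withdrawn". No minimum period is attached.
- **Analysis.** Section 4.16 is mainly descriptive and specifies no summary of refusal, adherence or AEs by arm.

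**The concern.** Whether an event happened and what caused it are separate questions, and the rule merges them. A patient who declines therapy for five days is left out of this count as soon as the team can offer another reason. Section 7.1.2 lists infections, pain and mood disturbance among expected events after stroke, so such reasons will often be to hand. Low mood could itself be how a less motivating approach shows up.

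Feasibility is the primary objective, and patient perceptions and retention are meant to inform a Phase III trial. A low refusal count could be read as evidence that the ILA is acceptable when it partly reflects how staff explained the refusals.

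**Working it through.** The documents give no refusal or AE rate, so there is no stated figure to reproduce. The check is a reading of the rule, followed by an illustration on assumed rates.

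**1. Direction within an arm.** Let p be the true proportion with a five-day refusal and s the share the team cannot otherwise explain. The counted proportion is p × s. Since s is at most 1, the count can equal the true number or fall below it, never exceed it.

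**2. Meaning in control units.** The rule stands under a heading about ILA events, while adherence monitoring covers all sites. If the rule applies in control units, there is no ILA to be the remaining explanation, so the second condition has no clear contrast. If it does not apply there, there is no control count. On either reading the AE counts are not like-for-like.

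**3. Illustration within one arm.** Assume n = 30 per arm (60 in total from section 4.13; no allocation ratio is stated) and ignore clustering. Expected count = n × p × s; P(at least one) = 1 − (1 − p × s)^n.

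| True p | s = 100% | s = 50% | s = 25% |
|---|---|---|---|
| 5% | 1.5; P = 0.79 | 0.75; P = 0.53 | 0.38; P = 0.31 |
| 10% | 3.0; P = 0.96 | 1.5; P = 0.79 | 0.75; P = 0.53 |
| 20% | 6.0; P > 0.99 | 3.0; P = 0.96 | 1.5; P = 0.79 |

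For example, with p = 10% and s = 25%: 30 × 0.10 × 0.25 = 0.75, and 1 − 0.975^30 = 0.53.

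**4. Illustration between arms.** Assume true rates of 20% (ILA) and 10% (control), a difference of 10 points.

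- s = 50% in both arms: 10% v 5%. The ratio stays 2:1 and the difference halves to 5 points.
- s = 50% v 100%: 20 × 0.50 = 10% v 10 × 1.00 = 10%. The difference vanishes.
- s = 25% v 75%: 5% v 7.5%. The sign reverses.
- s = 75% v 25%: 15% v 2.5%. The difference grows to 12.5 points.

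The bias in the difference therefore has no fixed direction.

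**5. Can session counts recover refusals?** Sessions received = sessions offered − sessions declined − sessions missed for other reasons. Sessions offered depend on unit frequency and length of stay, both of which vary by design. Sessions received alone therefore cannot separate refusal from a low-frequency unit or an early discharge. With 6–8 clusters, unit practice is also entangled with arm.

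**6. The five days.** Section 4.4.1 requires a therapy service on at least 5 days a week. Assuming a Monday-to-Friday service, five calendar days from Thursday to Monday hold three therapy days (Thursday, Friday, Monday). Five therapy days span five to seven calendar days. The plan does not say which is meant.

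**The case against.** The strongest reply is that the AE rule sits on top of adherence monitoring at every site, which carries no attribution condition. Raw adherence might therefore be compared whatever the AE count shows. That stands in part: a reader might infer that refusal cannot be compared with control at all, and the documents do not support that. The gap is narrower. The plan does not say how adherence is measured, that declined sessions and reasons are logged, or that they are summarised by arm.

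Explained refusals also do not leave the safety data entirely, because an infection, pain or mood disturbance is recorded under section 7.1.2. Sections 5.1 and 5.2 add patient interviews in both arms and therapist discussion groups. These sources give context, but neither supplies a refusal rate.

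The pilot is also small. Even unfiltered, 20% v 10% with 30 per arm has a 95% half-width of 1.96 × √(0.20 × 0.80/30 + 0.10 × 0.90/30) = 0.179, about 18 points before clustering. No definition would let this trial establish a doubling. That limits the inference but does not justify an incomplete count.

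Three further readings go too far:

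- A reader might take refusal to be the only harm tied to the ILA. Section 7.1.1 names another: "Withdrawal due to unanticipated/unexplained lack of progress in rehabilitation will be considered an AE". It carries a similar filter. Replacing it with a threshold on the mobility index is not warranted, since no criterion is available and blinded scores are already to be compared between groups (sections 4.12 and 4.16).
- A reader might infer that participants who lose capacity can never meet the five-day condition. Section 4.5.3.4 gives no timing for withdrawal, so five days of refusal could come first; it also calls such loss of capacity unlikely.
- A reader might infer that a near-zero count must follow or that a true doubling must disappear. An equal filter keeps the ratio: if 80% of 6 v 3 refusals are explained, 1.2 v 0.6 remain, still 2:1.

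**Conclusion.** The point holds in a limited form. Relatedness is built into the definition of the refusal AE and is judged by a team that, at ILA sites, knows the arm. As a count of five-day refusals, the figure in each arm is likely to be incomplete and cannot be too high. The counts are not like-for-like between arms, and the bias in their difference could go either way. These conclusions rest on the wording of section 7.1.1 and need no numerical assumption.

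The size is unknown. The illustrative figures depend on assumed refusal rates of 5–20%, 25–100% of refusals left unexplained, 30 per arm and no clustering. Separate adherence monitoring softens the problem but does not close it, because logging of offered and declined sessions is not specified. This is a cheap improvement worth making, not a defect that undermines the pilot.

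**What to change.** In both arms:

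- log each scheduled mobility session as offered, received or declined, with the reason for declining;
- count the refusal event whenever the first condition in section 7.1.1 is met, irrespective of cause;
- move the second condition out of the definition into a separate field for presumed cause and relatedness;
- state whether the five days are calendar days or scheduled therapy days;
- add to section 4.16 a descriptive summary by arm of declined sessions and refusal events.

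Sections 7.1.1 and 4.5.3.4 should also be reconciled so that refusals preceding a withdrawal are still recorded. This concerns recording only, not when a participant should be withdrawn.

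The cost is some extra case report form work, including an entry for sessions that did not take place, and rewording of section 7.1.1. More events will be counted, many of them not due to the ILA; the separate cause field keeps that visible.
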